## **6.5 Reporting of serious adverse events to the IRB and/or the Regulatory Authority**

The Lokelma Package Insert serves as the Reference Safety Information (RSI) for this study.

All SAEs occurring from the time of consent and during the study have to be reported, whether or not considered causally related to the study drug.

The Investigator or designated site personnel must inform the designated Sponsor representative immediately (**no later than 24 hours**) after becoming aware of an SAE occurring in their study patient.

SAE reports should be submitted to the Sponsor representative using the following contact details:

The designated Sponsor representative will work with the Investigator to ensure that all necessary information is collected **within 1 calendar day** of initial receipt for fatal and life threatening events **and within 5 calendar days** of initial receipt for all other SAEs.

For fatal or life-threatening adverse events where important/relevant information is missing, active follow-up must be undertaken immediately. The Investigator or designated site personnel must inform the Sponsor representatives of any follow-up information on a previously reported SAE immediately (**no later than 24 hours**) after receipt of the follow-up information.

Site PIs are responsible for informing the central Institutional Review Board (IRB) or their local IRB (as applicable) of SAEs as per their IRB requirements.

The Sponsor is responsible for informing the United States Food and Drug Administration (FDA), using the MedWatch/AdEERs form, of any serious or unexpected AEs that occur during the study, in accordance with the reporting obligations of 21 CFR 312.32. It is the responsibility of the Sponsor to compile all necessary information and ensure that submission of the safety report is completed within the FDA-mandated reporting timelines.

## **6.6 Reporting of Serious Adverse Events to Company**

The Sponsor (NephroNet) is responsible for informing the Company (AstraZeneca) of all SAEs occurring during the study, whether or not considered causally related to the investigational product (IP). SAEs assessed as related to the IP must be provided to the Company on an ongoing

basis as individual case reports. SAEs unrelated to the IP must be provided to the Company in the form of quarterly listings.

SAE files (individual case reports and line listings) should be submitted along with a cover page to the following designated Company email address:

[contact]

Suspected Unexpected Serious Adverse Reactions (SUSARs) must be reported to the Company at the same time these events are submitted to the FDA.

SAEs that do not require expedited reporting to the FDA/IRB still need to be reported to the Company as individual case reports on an ongoing basis (related SAEs) or provided in the form of quarterly listings (unrelated SAEs).

At the end of the study a final summary line listing of all SAEs submitted to the FDA and/or Company during the study, must be provided to the Company to enable reconciliation of safety information completed by the Company for its product.

## 6.7 Overdose

Overdose of the study drug (sodium zirconium cyclosilicate) (Lokelma®) could lead to hypokalemia. In case of suspected overdose (dosing above 15.0 g), potassium levels should be checked and potassium supplemented, as needed at the discretion of the PI.

The Investigator or designated site personnel must inform the Sponsor immediately (**no later than 24 hours**) of becoming aware of a study drug overdose.

For overdoses associated with a SAE, the standard reporting timelines apply, see [Section 6.4](#).

## 6.8 Pregnancy

All pregnancies and pregnancy outcomes should be reported to the Sponsor (NephroNet) and the Company (AstraZeneca) within the safety reporting guidelines.

### 6.8.1 Maternal exposure

If a patient becomes pregnant during the “high dialysate” treatment period, the study drug should be discontinued immediately.

Pregnancy itself is not regarded as an adverse event. However, congenital abnormalities/birth defects and spontaneous miscarriages should be reported and handled as SAEs. Elective abortions without complications should not be handled as AEs. The outcome of all pregnancies (spontaneous miscarriage, elective termination, ectopic pregnancy, normal birth, or congenital abnormality) should be followed up and documented even if the patient was withdrawn from the study.

The Investigator or designated site personnel must inform the Sponsor immediately (**no later than 24 hours**) of becoming aware of a pregnancy occurring in the study. All relevant pregnancy information should be provided to the Sponsor within 1 or 5 calendar days for SAEs (see [Section 6.4](#)) and within 30 days for all other pregnancies. The same timelines apply when pregnancy outcome information becomes available.

## 6.8.2 Paternal exposure

Not applicable. There will be no requirements or restrictions associated with paternal exposure.

## 6.9 Management of IP-related Toxicities / Dose Reductions

The study drug (Lokelma) will be titrated from 5.0 grams per day (4 days/week) up to a maximum of 15.0 grams per day (4 days/week), to maintain  $K^+$  within the desired target range (between 4.0 and 5.5 mEq/L). potassium levels will be regularly monitored, and the study drug dose adjusted based on the potassium levels (i.e., increased [up to a maximum of 15.0 grams/day] if potassium is  $>5.5$  mEq/L, or decreased if potassium is  $<4.0$  mEq/L).

As described in [Section 3.9](#), the study drug will be permanently discontinued in case the patient develops any of the following IP-related events:

- Two (2) or more hypokalemic events (defined as pre-dialysis  $K^+$  level of  $<3.5$  mEq/L);  $<$

Refer to [Section 3.9](#) for further details on events requiring permanent discontinuation of the study drug.

Safety protocols for the management of intra-dialytic events are provided in [Section 5.3](#).

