### **3.9 Discontinuation of Investigational Product**

Patients may be discontinued from investigational product (IP) in the following situations:

- Patient decision. The participant is at any time free to discontinue treatment, without prejudice to further treatment;
- Incorrectly randomized participant where violation of the inclusion/exclusion criteria would put the participant at undue risk;
- Adverse event for which the investigator judges continued treatment may put the participant at undue risk;
- Pregnancy;
- Development of any of the following study-specific criteria for discontinuation:
  - Permanent atrial fibrillation, as determined by echocardiogram or cardiology assessment;

- Requiring for permanent placement of a cardiac pacemaker or AICD;
  - Refractory hyperkalemia ( $K^+ > 6.5$  mEq/L) while on 15 grams 4 days per week of Lokelma;
  - Hypokalemic event (defined as pre-dialysis  $K^+$  level of  $< 3.5$  mEq/L): Patients experiencing a minimum of two (2) hypokalemic events while taking Lokelma will have their Lokelma adjusted or discontinued at the discretion of the site PI;
  - Renal transplant.
- Severe non-compliance with the study protocol.

Note: patients wishing to remain in the study on treatment despite developing an adverse event may do so at the site PI's discretion, unless they remain hyperkalemic with  $K^+ > 6.5$  mEq/L after a long inter-dialytic interval (LIDI) for two (2) consecutive weeks.

Regardless of the reason for discontinuation, all reasons for discontinuation of study treatment must be documented in the electronic case report form (eCRF).

If the patient is discontinued from investigational product, the scheduled study visits, data collection and procedures should continue according to the study protocol until study completion, unless the patient withdraws consent for any further study procedures and follow-up. The approach taken should be documented in the eCRF.

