### **3.9.1 Procedures for Discontinuation of a Patient from Investigational Product**

At any time, patients are free to discontinue investigational product or withdraw from the study (i.e., investigational product and assessments – see [Section 3.10](#)), without prejudice to further treatment. Patients deciding to discontinue the investigational product will be asked to: (i) provide the reason(s) for discontinuation, including the development of any adverse event(s) contributing to their decision; (ii) return to the clinic for the remaining study visit(s) and assessment(s); and (iii) return all unused study drug to the site. Adverse events will be followed up, as described in [Section 6](#).

The investigational product (Lokelma) can be discontinued abruptly (without the need for gradual treatment stepdown or tapering). Patients may be allowed to re-start the investigational product at the discretion of the site PI.

Patient withdrawal from study is described in [Section 3.10](#).

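### Repeated hypokalemia means a mandatory permanent stop of Lokelma in Section 6.9, but a discretionary dose change or stop in Sections 3.9 and 5.3.1, with restart allowed in 3.9.1

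*Protocol*

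**What the plan says.** Section 6.9 states that "the study drug will be permanently discontinued in case the patient develops any of the following IP-related events". The one event it lists is "Two (2) or more hypokalemic events (defined as pre-dialysis" K+ below 3.5 mEq/L). It presents this as a restatement of Section 3.9, and then sends the reader to 3.9 "for further details on events requiring permanent discontinuation of the study drug".

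Section 3.9 opens in permissive terms: "Patients may be discontinued from investigational product (IP) in the following situations". Under its study-specific criteria it defines the hypokalemic event in the same way (pre-dialysis K+ below 3.5 mEq/L). It then says that patients with at least two "hypokalemic events while taking Lokelma will have their Lokelma adjusted or discontinued at the discretion of the site PI". Nowhere does it describe stopping the drug as permanent.

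Section 5.3.1, the safety protocol for potassium abnormalities, gives the same trigger and the same discretionary action as 3.9.

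Section 3.9.1 adds: "Patients may be allowed to re-start the investigational product at the discretion of the site PI". No reason for stopping is excepted.

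**The concern.** One clinical trigger leads to two different instructions. Section 6.9 leaves the investigator no choice and makes the stop irreversible. Sections 3.9 and 5.3.1 leave the choice to the investigator and include keeping the patient on the drug at another dose. Section 6.9 also misreports its own source, so following its cross-reference leads to the opposite rule.

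Treatment-associated hypokalemia, with possible worsening of arrhythmia, is the first risk listed in Section 1.3, and Lokelma-induced hypokalemia is Safety Objective #1. The synopsis marks a data monitoring committee as not applicable, and Section 6.10 says no study committees will be set up. The written rule therefore carries much of the protection, and about 10 to 12 sites have to apply it.

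The choice of rule also affects how long such patients take Lokelma in the experimental period, which adverse events are recorded, and which actions count as protocol deviations.

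**Working it through.** No figure is involved, so the check is a comparison of the four sections.

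| Section | Trigger | Action | Binding? | Reversible? |
|---|---|---|---|---|
| 6.9 | At least two events, pre-dialysis K+ < 3.5 mEq/L | Stop Lokelma | Mandatory | No |
| 3.9 | Same | Change dose or stop | Investigator decides | Not stated |
| 5.3.1 | Same | Change dose or stop | Investigator decides | Not stated |
| 3.9.1 | Any stop of the drug | Restart allowed | Investigator decides | Yes |

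A site has three possible actions once the trigger is met:

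1. **Stop for good.** Complies with 3.9, 5.3.1 and 6.9.
2. **Stop, then restart.** Complies with 3.9, 5.3.1 and 3.9.1; breaches 6.9.
3. **Change the dose.** Complies with 3.9 and 5.3.1; breaches 6.9.

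Two of the three actions are thus both allowed and forbidden. Section 9.2.4 requires all deviations to be documented, so whether these actions are deviations depends on the section consulted.

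**Effect on adverse-event counts.** Take a patient with two qualifying values, no symptoms and no seriousness criterion met. Section 6.4.6 makes a worsened protocol-mandated laboratory value an adverse event only if it meets a seriousness criterion or is the reason study treatment was stopped. A site following 6.9 stops the drug, so the value becomes an adverse event and enters the Section 8.5.6 summary of adverse events leading to discontinuation of Lokelma. A site that changes the dose under 3.9 records no adverse event for the same patient. Adverse-event frequency is the outcome of Safety Objective #3.

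**Effect on exposure.** Section 3.9 keeps patients who stop the drug in scheduled visits and data collection, and Section 8.3.2 analyses them as randomized. Their experimental-period data therefore stay in the analysis, with Lokelma continuing under one reading and absent under the other. That can affect later potassium results, including further hypokalemic events counted for Safety Objective #1.

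**Opportunity for the trigger.** Footnote 1 of Table 1 schedules weekly pre-dialysis K+ in the 2-week accommodation period and the 8-week treatment phase, so up to 2 + 8 = 10 scheduled values in the experimental period. The protocol gives no rate of values below 3.5 mEq/L, so an expected number of affected patients cannot be calculated.

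**The case against.** The case on the other side has five parts.

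- **The rules overlap.** Permanent discontinuation is one of the options in 3.9 and 5.3.1, so a site that stops the drug for good satisfies every section. This is correct, but it does not reconcile the sections: the other permitted actions still breach 6.9.
- **The restart sentence in 3.9.1 is general.** It could be read as the rule, with 6.9 as a specific exception. This has force. The direct conflict is 6.9 against 3.9 and 5.3.1, and 3.9.1 is supporting evidence. Even so, 3.9.1 states no exception, and a restart cannot coexist with a permanent stop.
- **Few patients may be affected.** Entry requires two pre-dialysis values of 5.1 to 6.5 mEq/L, any screening value below 4.6 excludes, the experimental bath has the higher potassium, and the dose is already reduced below 4.0. These features suggest, without proving, that two values below 3.5 would be uncommon. This limits the size of the problem but does not remove the contradiction.
- **Some consequences are not spelled out in the protocol.** It does not say which bath a patient receives after stopping Lokelma. Stopping the drug is also not withdrawal from the study, so the count of withdrawals due to adverse events is not the direct link. The link that stands is through Sections 6.4.6 and 8.5.6.
- **Much of the recording already exists.** Reasons for discontinuation (3.9), drug administration (7.5) and action taken for each adverse event (6.4.3) are collected. That leaves little to add.

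**Conclusion.** The point holds. Section 6.9 contradicts 3.9 and 5.3.1 on the same trigger, cites 3.9 for a rule that 3.9 does not contain, and is incompatible with the unrestricted restart in 3.9.1. All four are current body text, and the version history does not explain the difference. A separate analysis plan could not settle it, because it is a treatment rule.

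The number of patients affected is unknown and may be small. For each one, the readings can differ by all the Lokelma dosing left in that period, at four dosing days a week, and by whether an adverse event leading to discontinuation is recorded. Sample size, power and the primary analysis set are unaffected. The adverse-event consequence assumes an asymptomatic, non-serious case and sites that apply 6.4.6 as written. Which rule is clinically right is not judged here.

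**What to change.** Reconcile Sections 3.9, 3.9.1, 5.3.1 and 6.9 so that a single rule for repeated hypokalemia appears in the same terms throughout. The rule is for the sponsor's clinicians to choose. It should state whether stopping is mandatory or discretionary and whether restart is possible afterwards. Correct the statement in 6.9 about what 3.9 says.

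Record in the eCRF which action followed the second event. Most of this is already collected; the likely gap is a dose change with no associated adverse event.

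The cost is a few sentences across four sections of one amendment, with IRB approval under Section 10.5 if the change is substantial, and at most one eCRF item. No patients, visits or samples are added.

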## 6.10 Study Governance and Oversight

Responsibilities for the study design, protocol development, scientific oversight, and coordination of the study rest with the NephroNet as the responsible Academic Research Organization (ARO), and the National Coordinating PI ([name]).

No study committees will be established. Given the open label study design, and the underlying condition involving the management of routine and frequent complications of dialysis, site PIs will be responsible for all emergency medical decisions related to their study patients. Site PIs will meet with the National Coordinating PI on quarterly basis to review safety data and determine if changes to the protocol design or study conduct are required.

## 7. INVESTIGATIONAL PRODUCT AND OTHER TREATMENTS

### 7.1 Identity of Investigational Product(s)

The investigational product (IP) in this study is sodium zirconium cyclosilicate (Lokelma®), a potassium binder product for oral administration. It is indicated for the treatment of hyperkalemia in adults (*Lokelma United States Prescribing Information [USPI], 19th October 2021*).

Lokelma, powder for oral suspension will be supplied in 5.0 gram packets to study participants.

Investigational product	Dosage form and strength
sodium zirconium cyclosilicate (Lokelma ® )	For oral suspension: 5 g of white to grey powder in a foil-lined packet.

Note: In this protocol, the terms investigational product, IP, and study drug are used interchangeably.

## 7.2 Dose and Treatment Regimens

### 7.2.1 Dosing Regimen

Patients will take Lokelma supplementation on off-dialysis days (4 days/week) while receiving hemodialysis with 3.0 K+/2.5 Ca++ mEq dialysate bath (8-week treatment phase):

- Patients on a Monday-Wednesday-Friday dialysis schedule will take the study drug on Tuesday, Thursday, Saturday, and Sunday
- Patients on a Tuesday-Thursday-Saturday dialysis schedule will take the study drug on Monday, Wednesday, Friday, and Sunday.

The individual starting dose will be 5.0 grams (4 days/week), and will be titrated weekly in 5.0 gram increments up to a maximum of 15.0 grams (4 days/week) to maintain K+ within the desired target range (between 4.0 and 5.5 mEq/L):

- Patients who fail to achieve a pre-dialysis K+ of  $\leq 5.5$  mEq/L after one week of 5.0 grams Lokelma will be treated with 10.0 grams on off-dialysis days for an additional 7 days.
- Patients failing to achieve a pre-dialysis K+ of  $\leq 5.5$  mEq/L after one week of 10.0 grams Lokelma will have their study drug dose increased to 15.0 grams.
- Patients failing to achieve the target K+ after a 7-day course of 15.0 grams Lokelma on off-dialysis days will be considered a treatment failure and withdrawn from the study.

Potassium levels will be regularly monitored throughout the 8-week treatment phase, and the study drug dose adjusted based on the potassium levels (i.e., increased [up to a maximum of 15.0 grams/day] if potassium is  $>5.5$  mEq/L, or decreased if potassium is  $<4.0$  mEq/L).

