**Table 1 Study Plan and Schedule of Assessments**

Study Period / Visit	Screening	ILR Insertion by EP cardiologist	Baseline/ Randomization	New Dialysate Accommodation Period 1	Treatment Phase 1	Cross-over	New Dialysate Accommodation Period 2	Treatment Phase 2	ILR Removal by EP cardiologist	End of Study	Reference to Protocol Section
Study Week (Wk) [* , ** or ***]	-4 to -3**	-2*	1**	1 & 2**	3 to 10**	11**	11 & 12**	13 to 20**	21-22*	22-23***	
Study Day (D)	-28 to -15	-14	1	1 to 14	15 to 70	71	71 to 84	85 to 140	Between D141 and D155	Within 1 to 14 days after ILR Removal	
Day of the week			M/T	M/T	M/T	M/T	M/T	M/T			
Written informed consent	X										4.1.1
Assignment of unique Screening Number	X										4.1.2
Demographics	X										4.1.3
Medical/surgical & Medication history	X										4.1.4
Physical examination	X										4.1.5
Vital signs and weight measurements	X			X	X		X	X		X	4.1.6
12-lead ECG	X										5.2.3.1
K+ Piccolo POCT (pre-dialysis) [1]	X			X	X		X	X			4.1.7 4.2.1

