**Table 1 Study Plan and Schedule of Assessments**

Study Period / Visit	Screening	ILR Insertion by EP cardiologist	Baseline/ Randomization	New Dialysate Accommodation Period 1	Treatment Phase 1	Cross-over	New Dialysate Accommodation Period 2	Treatment Phase 2	ILR Removal by EP cardiologist	End of Study	Reference to Protocol Section
Study Week (Wk) [* , ** or ***]	-4 to -3**	-2*	1**	1 & 2**	3 to 10**	11**	11 & 12**	13 to 20**	21-22*	22-23***	
Study Day (D)	-28 to -15	-14	1	1 to 14	15 to 70	71	71 to 84	85 to 140	Between D141 and D155	Within 1 to 14 days after ILR Removal	
Pregnancy Test for Females of Childbearing Potential	X										

Abbreviations: AE=adverse event; Ca=calcium; ECG=electrocardiogram; EP=electrophysiologist; ILR=insertable loop recorder; K=potassium; Mg++=magnesium; PBUTs=protein-bound uremic toxins [including p-Cresol sulfate [PCS], indoxyl sulfate, and asymmetric dimethylarginine [ADMA)]; SAE=serious adverse event

\*Performed on any day. (Note: ILR placement needs to be one week prior to baseline, which starts on Mondays or Tuesdays after each long dialysis weekend.)

\*\*Performed weekly, on Mondays or Tuesdays after each long dialysis weekend. (Note: Screening ICF can be obtained on any dialysis day, but all other procedures need to be performed on Monday or Tuesdays after the long dialysis weekend. Additionally, consenting may be conducted several weeks prior to other study procedures depending on the need for a prohibited medication washout or whether the consenting process occurred on a day other than the Monday or Tuesday after the long dialysis weekend.)

\*\*\*Performed on any dialysis day

[1] K+ Piccolo POCT (utilizing full renal panel) are performed pre-dialysis, on a Monday or Tuesday after the long dialysis weekend, twice during the Screening period, and weekly during the treatment period (both 2-week accommodation periods and 8-week Treatment phases). Note: K+ Piccolo POCT may be performed several weeks after consenting depending on the need for a prohibited medication washout or whether the consenting process occurred on a day other than the Monday or Tuesday after the long dialysis weekend.

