[2] During the treatment period (both 2-week accommodation periods and 8-week Treatment phases), a second Piccolo POCT is performed promptly before dialysis end and within 30 minutes prior to rinse back on Mondays or Tuesdays after each long dialysis weekend (i.e., weekly), to measure K+, Ca++ and PO4.

[3] Applies only to the first twenty-five (25) patients randomized receiving standard treatment (hemodialysis using 2.0K+/2.5 Ca++ dialysate bath, without Lokelma supplementation) during Treatment Phase-1. Performed weekly, on Mondays or Tuesdays after each long dialysis weekend, promptly before dialysis end and within 30 minutes prior to rinse back.

[4] Performed weekly, on Mondays or Tuesdays after each long dialysis weekend, promptly before dialysis end and within 30 minutes prior to rinse back. Mg++ levels will be determined by the local laboratory at each site.

[5] Performed (if possible) upon symptomatic muscle cramping, promptly before dialysis end and within 30 minutes prior to rinse back. Mg++ levels will be determined by the local laboratory at each site.

[6] Baseline/Randomization is conducted on Week 1 of the new Dialysate Accommodation Period 1. Crossover occurs on the same day as Week 11 of the new Dialysate Accommodate Period 2. Neither Baseline/Randomization nor Crossover will be considered a separate visit.

[7] If ILR insertion is performed more than 30 days after the last K+ Piccolo POCT determination, please contact the sponsor who will determine if an additional K+ Piccolo POCT determination will be required prior to the baseline visit. These will be handled on a case-by-case basis.

[8] Adverse events will be collected from the time of first dose of Lokelmaâ, throughout the treatment and post-treatment follow-up period, up to the last study visit.

[9] SAEs will be reported from the time the patient signed the Informed Consent Form.

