### 4.2.1 Blood Draws (Weeks 3 to 10 and Weeks 13 to 20)

During both 8-week treatment phases, the first twenty-five (25) patients randomized receiving standard treatment (hemodialysis using 2.0K+/2.5 Ca++ dialysate bath, without Lokelma supplementation) will undergo blood collection for select chemistry tests and determination of protein-bound uremic toxins (PBUTs).

Blood will be drawn as follows:

- 1) A 4.0 ml Green Top tube will be drawn from the dialysis line after placement of the dialysis needles and BEFORE the initiation of dialysis. The Green Top tube will be in & out inverted 3 times and then used for Piccolo POCT measurements of K+, Ca++ and PO4, as described in [Section 8](#). This will be repeated promptly before the anticipated termination of the dialysis session and within 30 minutes prior to rinse back.
- 2) Treatment Phase-1 only: Two 4.0 ml Purple Top tubes will be drawn from the first twenty-five (25) patients receiving standard treatment (hemodialysis using 2.0K+/2.5 Ca++ dialysate bath, without Lokelma supplementation) by the same method (as described above) and centrifuged. Each tube of plasma (approximately 1ml after processing) will be transferred to a 1.0 ml O-Ring sealed cryovials (two cryovials pre-dialysis and two cryovials promptly before the anticipated termination of the dialysis session and within 30 minutes prior to rinse back) and frozen at -80°C until analyzed for measurement of pre- and post-dialysis concentrations of the following PBUTs: p-Cresol sulfate (PCS), indoxyl sulfate, and asymmetric dimethylarginine (ADMA). Measurement of pre- and post-dialysis levels will be conducted by an outside vendor using gas chromatography-mass spectrometry (GC-MS) ([Tsikas et al. 2003](#)).
- 3) 5) A 5.0 ml Yellow Top SST tube will be drawn from the dialysis line promptly before the anticipated termination of the dialysis session (and within 30 minutes prior to rinse back) will be sent to the local laboratory for routine measurement of Mg++ levels.
- 4) A 2nd 4.0 ml Green Top tube will be drawn from the dialysis line promptly before the anticipated termination of the dialysis session (and within 30 minutes prior to rinse back) for Piccolo POCT measurement of post-dialysis electrolytes (K+, Ca++ and PO4), as described in [Section 8](#).

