**Figure 10 – Patient Assistant**

### **4.2.3 Cross-Over (Week 11)**

At the end of the first treatment phase (Weeks 3 to 10) of the study, all blood draws will be stopped for 2 weeks. Cardiac loop recording devices will not be interrogated during this 2-week accommodation period, and the data recorded during that time will not be used for analysis. Patients who completed treatment with experimental 3.0 K+/2.5 Ca++ dialysate with Lokelma supplementation (on off-dialysis days) during Treatment Phase-1 will be crossed over to standard 2.0 K+/2.5 Ca++ dialysate with no Lokelma supplementation for Treatment Phase-2. Patients who completed treatment with standard 2.0 K+/2.5 Ca++ dialysate with no Lokelma supplementation during Treatment Phase-1 will cross-over to experimental 3.0 K+/2.5 Ca++ dialysate with Lokelma supplementation (on off-dialysis days) for Treatment Phase-2.

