### 5.1.3 Potassium Measurements

A further secondary objective of the study (see [Section 2.2](#)) is to determine whether the addition of oral sodium zirconium cyclosilicate (Lokelma®) during the 2-month treatment phase with the 3.0 K+/2.5 Ca++ dialysate bath will reduce the number of days outside the “K+ safety range” of 4.0 to 5.5 mEq/L compared to the 2-month treatment phase with the 2.0 K+/2.5 Ca++ dialysate bath.

K+ Piccolo POCT will be performed weekly during the two 8-week Treatment phases, as follows: pre-dialysis, and promptly before dialysis termination and 30 minutes prior to rinse back (along with Ca++ and PO4 measurements); see [Section 4.2.1](#).

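### Section 4.2.3 stops all blood draws in Weeks 11–12, where Table 1 requires weekly tests and Section 7.2.1 needs the Day 78 K+ for its first dose step

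*Protocol*

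**What the plan says.** **Text that requires testing in Weeks 11–12.** Table 1 marks the pre-dialysis Piccolo K+ row in both accommodation periods. Note [1] makes the test "weekly during the treatment period (both 2-week accommodation periods and 8-week Treatment phases". Note [2], on the second Piccolo test near the end of the session, uses the same scope: "During the treatment period (both 2-week accommodation periods and 8-week Treatment phases". The table also marks end-of-dialysis Mg++ in both accommodation periods.

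**Text that stops it.** Section 4.2.3 says that at the end of the first treatment phase "all blood draws will be stopped for 2 weeks". Those two weeks are Weeks 11 and 12, which Table 1 calls accommodation period 2.

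**Text with a narrower week range that stops nothing.** The heading of Section 4.2.1 reads "Blood Draws (Weeks 3 to 10 and Weeks 13 to 20". Section 4.2 describes the weekly draws just after it mentions the end of accommodation. In Section 5.1.3, K+ "Piccolo POCT will be performed weekly during the two 8-week Treatment phases". In Section 7.2.1, "Potassium levels will be regularly monitored throughout the 8-week treatment phase, and the study drug dose adjusted based on the potassium levels". Section 6.9 gives the same adjustment rule without an 8-week limit.

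**Text that needs the value.** Under Section 7.2.1, a patient whose pre-dialysis K+ is still above 5.5 mEq/L "after one week of 5.0 grams Lokelma will be treated with 10.0 grams on off-dialysis days". A week later the dose goes to 15 g, and a week after that the patient is a treatment failure. The Synopsis (Duration of treatment) and the dispensing row of Table 1 both put Lokelma in use from the start of accommodation.

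**The concern.** A site that reaches Week 11 has two current, explicit instructions that exclude each other. Section 9.2.4 does not let sites depart from the protocol without approval, so whichever instruction a site follows, it departs from the other.

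The lost test has a job. Patients qualify with pre-dialysis K+ of 5.1–6.5 mEq/L (Section 3.1). They then move to a bath with more potassium on the lowest binder dose. Section 1.2 lists the accommodation period and K+-guided titration among the measures that limit risk, and says that patients with persistently high K+ are unlikely to tolerate the higher bath. Section 6.10 sets up no study committee and provides for quarterly safety review, so the weekly K+ at the site is the main safeguard in the first weeks on the new bath.

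**Working it through.** The protocol gives no figure to reproduce, so the check is calendar arithmetic on Table 1.

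**Inputs**
- The first day of Week n is 7 × (n − 1) + 1. This matches Table 1: Week 3 = Day 15, Week 11 = Day 71, Week 13 = Day 85.
- Draws are weekly, on the Monday or Tuesday after the long interval (Table 1).
- The 3.0 K+ bath and Lokelma 5 g start at Week 11, Day 71, for the sequence that has the 2.0 K+ bath first (Sections 3.5 and 4.2.3; Synopsis).
- Dose steps follow a pre-dialysis K+ after one week at each dose (Section 7.2.1).
- 88 patients are randomized 1:1, so 88 / 2 = 44 are in this sequence.

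**Scheduled pre-dialysis draws**
- Table 1: Day 64 (Week 10), 71, 78, 85, 92, 99.
- Section 4.2.3: Days 71 and 78 drop out, which leaves Day 64, 85, 92, 99.

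The Day 71 pre-dialysis sample is taken before the first 3.0 K+ session, so it still reflects the old bath. Even under Table 1, the first on-bath value is Day 78.

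**Patient whose K+ stays above 5.5 mEq/L**

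| | Table 1 | Section 4.2.3 |
|---|---|---|
| First on-bath pre-dialysis K+ | Day 78 | Day 85 |
| Interval between scheduled pre-dialysis values | 7 days | 85 − 64 = 21 days |
| Time at 5 g before the first decision | 78 − 71 = 7 days, 4 doses | 85 − 71 = 14 days, 8 doses |
| Step to 10 g | Day 78 | Day 85 |
| Step to 15 g | Day 85 | Day 92 |
| Treatment failure | Day 92 | Day 99 |
| Weekly K+ visits in Weeks 11–20 | 10 | 8 |

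Each step is 7 days later under Section 4.2.3. The net loss for titration is one on-bath pre-dialysis value, Day 78. The end-of-dialysis values on Days 71 and 78 are also lost, although Section 7.2.1 does not titrate on those.

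**The other sequence at Week 11.** These patients move to the 2.0 K+ bath without Lokelma. Section 4.2.3 removes their Table 1 tests too, but no dose decision depends on them.

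**Weeks 1–2.** Table 1 requires weekly tests, and no sentence stops them. The ranges in Sections 4.2, 4.2.1 and 7.2.1 say where testing takes place without saying that it does not take place earlier. This is loose wording and not a second contradiction.

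**The case against.** The strongest reply is that Table 1 already governs. Section 4 refers to it for the schedule, Section 4.2 opens by sending treatment-period assessments to it, and Section 5.2.1 does the same for chemistry samples. This makes Table 1 the natural default and the right text to keep. It does not cancel Section 4.2.3, which is the specific instruction for the crossover and sits inside Section 4.2. Nothing says which text prevails.

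A second reply is that routine clinic samples would fill the gap. They may, but the protocol schedules none for this purpose. Section 4.2.3 also stops draws without qualification, whereas Section 4.3 stops only those outside standard care.

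A third reply is that Section 5.1.3 is about sampling for an efficacy endpoint, and that Section 7.2.1 does not rule out earlier monitoring. Both points stand. The conflict between Table 1 and Section 4.2.3 does not need either section.

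A reader might also infer more than the text supports:
- *The rule in Section 3.9 on K+ above 6.5 mEq/L for two consecutive weeks is disabled in Weeks 11–12.* Under Table 1, two consecutive on-bath values (Days 78 and 85) first exist on Day 85, so the rule could not be met on that bath within those weeks under either text.
- *Patients go unmonitored for 14 of 70 days on the bath.* That figure is not net of Table 1, which itself has no on-bath pre-dialysis K+ before Day 78.
- *Delayed titration contaminates the counted atrial fibrillation window.* Under Table 1 the 15 g step also falls on Day 85, the first counted day, and Section 7.2.1 adjusts doses throughout the phase. The share of patients who need 15 g and the share of sites that would follow Section 4.2.3 are not given.
- *The 8-week label on dosing in Section 7.2.1 withholds binder during accommodation.* The same sentence ties intake to receiving the 3.0 K+ bath, and Table 1 dispenses drug in those weeks.

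**Conclusion.** The contradiction is real, and it is confined to Weeks 11–12: Section 4.2.3 against Table 1 with its notes [1] and [2]. It matters for the sequence that crosses to the 3.0 K+ bath at Week 11, about 44 of 88 planned patients. At a site that follows Section 4.2.3, these patients lose the Day 78 value that the first titration step needs, wait 21 days instead of 7 between scheduled pre-dialysis values, and reach every dose decision 7 days later. At a site that follows Table 1 nothing is lost.

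The calendar assumes that the bath and the 5 g dose start on Day 71 and that dose decisions are made on the weekly draw day. The count of 44 assumes full enrollment at exactly 1:1, and is an upper limit in that not every site need follow Section 4.2.3.

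This is a safety and conduct problem that should be corrected. It does not touch power, alpha or the 8-week endpoint windows, and no effect on atrial fibrillation counts is claimed.

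**What to change.** Make Table 1 the rule.

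1. **Section 4.2.3:** replace the sentence on stopping draws with: *Weekly pre-dialysis and end-of-dialysis Piccolo tests (K+, Ca++, PO4) and end-of-dialysis Mg++ continue in Weeks 11 and 12 as in Table 1; ILR interrogation is not done, and data from these weeks are not used for the efficacy endpoints.*
2. **Section 4.2:** reword the paragraph on weekly draws so that they start in the first week on the assigned bath and not after accommodation.
3. **Section 4.2.1:** change the heading and the opening sentence to cover the accommodation weeks, and keep PBUT sampling in Treatment Phase-1 only.
4. **Section 7.2.1:** extend the monitoring and dose-adjustment sentence so that weekly K+ and titration run from the first week on the 3.0 K+ bath.

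The cost is wording in four sections, which one amendment can carry. It adds no draw beyond those already in Table 1, and it leaves the design, the endpoint windows and the sample size unchanged.
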